4.0 METHODOLOGY

4.1 **Outcomes**

Primary outcomes

- Dose-limiting toxicity (See section 4.4.2 Dose modification)
- Clinical benefit rate (CBR): CR + PR + SD (>24weeks)

Secondary outcomes

- Overall objective response (ORR): % of the patients who achieve CR or PR.
- Time to progression (TTP): the time from starting grapiprant treatment until objective tumor progression (PD).
- Duration of response of the proposed treatment (Phase 2 only): the time from observing the response to the grapiprant treatment until objective tumor progression (PD)
- Time to first response of the proposed treatment (Phase 2 only): the time from starting grapiprant treatment until observing the response.
- Progression-free survival (PFS): the time from starting grapiprant treatment until objective tumor progression (PD) or death with any cause.
- Overall survival (OS): the time from starting grapiprant treatment until death with any cause.
- Association between the treatment response and the urine prostaglandin E2 metabolite in urine samples after the proposed treatment.

Exploratory outcome

• Change in 1) immune cell markers (M1/M2 macrophage, T lymphocyte, regulatory T cell, myeloid-derived suppressor cell, NK cell, dendritic cell, endothelial cell, fibroblast). 2) PD-L1, PD-1, and ALDH1 on tumor and immune cells.

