4.3 Study Design

[figure not shown]
The design of this study is a single-arm, phase Ib/II study. The overview of the study is shown in **Figure 1**. A total of 25 patients will be enrolled in the study. Once the recommended phase II dose of grapiprant in combination with eribulin is determined, the remaining patients will be treated in the phase II portion, which adds 14 ± 2 days window period of grapiprant treatment alone before the main study to evaluate the effect of grapiprant treatment in the tumor microenvironment and urine prostaglandin E2 metabolite. We will perform a correlative study by collecting tumor and urine samples at pre-and post-window periods. We will ensure the safety of grapiprant and eribulin combination by phase Ib part and determine efficacy in the phase II part—the detail of the trial design described in the **statistical analysis plan (7.0)**.

The starting dose of grapiprant will be 300 mg BID daily orally. Eribulin will be intravenously administered on day 1 and day 8 of every cycle (starting at the FDA-approved dose of 1.4 mg/m²). We define one cycle as 21 days. We will continue the treatment until disease progression, discontinuation by severe toxicity, death, and patient withdrawal. If the patients cannot continue the eribulin because of its toxicity, they will stop eribulin but continue grapiprant as a single treatment until progression or discontinuation. If the patients cannot continue the grapiprant because of its toxicity, they will be off treatment. We will follow-up with the patients up to 5 years after off-treament (see section 4.9). The follow-up can be performed in the clinic in MD Anderson Cancer Center. If the patient is unwilling to come to the clinic, the follow-up would be done by phone.

We will perform imaging analysis by PET-computed tomography (CT) or CT/bone scan at baseline, after the 2 cycles of proposed treatment (does not includes window period), then at the end of every 3 cycles. The Quantitative Imaging Analyzing Core (QIAC) in MD Anderson Cancer Center will independently evaluate the treatment response based on the imaging results.

Protocol 2021-0077 PI: [name] **Proprietary Information of MD Anderson**

Co-PI: [name] Date: 11/22/2022

Product: Grapiprant

Protocol 2021-0077 Proprietary Information of MD Anderson

PI: [name] Co-PI: [name] Date: 11/22/2022

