We will administer eribulin with 1.4mg/m^2 on day 1 and day 8 in every cycle. We will assess eribulin's adverse reactions by obtaining the blood sample and physical examination, especially for peripheral neuropathy. We will not administer eribulin on day 1 or day 8 in patients with \geq grade 3 neutropenia, \geq grade 2 thrombocytopenia, or grade 3/4 nonhematologic toxicities. The day 8 dose may be delayed for up to 1 week in patients with toxicities. If toxicities resolve or improve to grade 2 or less by day 15, we will administer eribulin at a reduced dose and initiate the next cycle no sooner than 2 weeks later. If toxicities do not resolve or improve to grade 2 or less by day 15, we will omit the dose. If a dose has been delayed for toxicities that have recovered to the severity of grade 2 or less, resume the recommended reduced dose. If a dose has been reduced due to toxicities, we will not re-escalate.

Table 3. Recommended eribulin dose modifications and criteria for treatment interruption and re-initiation with treatment-related adverse events

DOSE MODIFICATIONS FOR ERIBULIN						
Toxicity (CTCAE 5.0 Eribulin Dose Modifications Grade)						
HEMATOLOGICAL						
Neutropenia (ANC)						
$ANC < 500/mm^3 \text{ for } > 7 \text{ days or}$						
$ANC < 1,000/mm^3$ with fever or	Hold eribulin until ANC is $\geq 1,000$ and platelet count is ≥ 75 x					
infection	10 ⁹ /L, then decrease 1 dose level permanently					

Protocol 2021-0077 Proprietary Information of MD Anderson PI: [name]

Co-PI: [name] Date: 11/22/2022

Any event requiring permanent dose reduction while receiving 1.1 mg/m ²	Hold eribulin until ANC is $\geq 1,000$ and no fever, then decrease 1 dose level
Any event requiring permanent dose reduction while receiving 0.7 mg/m ²	Discontinue eribulin
Anemia (Hemoglobin)	
Grade 1	Maintain dose level and continue eribulin with caution
Grade 2	Hold eribulin until hemoglobin is Grade 1.
Grade 3-4	Hold eribulin until hemoglobin is Grade 1, then decrease 1 dose level
Thrombocytopenia (Platelet)	
Platelets < 25,000/mm ³ or platelets < 50,000/mm ³ requiring transfusion	Hold eribulin until platelet (g/dL) is \geq 100,000, then decrease 1 dose level permanently
Any event requiring permanent dose reduction while receiving 1.1 mg/m ²	Hold eribulin until platelet (g/dL) is \geq 100,000, then decrease 1 dose level
Any event requiring permanent dose reduction while receiving 0.7 mg/m ²	Discontinue eribulin
NEUROLOGICAL	
Peripheral neuropathy	

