4.9.1. Definition of Treatment Response

We will perform imaging analysis by CT scan, bone scan, or PET-CT. If the patient had a locoregional disease, a mammogram and ultrasound would be considered. We will evaluate the treatment response in metastasis sites (and primary site, if it exists) and at the following time points: 1) baseline 2) after 2 cycles of proposed treatment (does not include window period) 3) every 3 cycles of proposed treatment. All imaging analysis will be performed based on RECIST criteria. The efficacy outcomes will be CBR, ORR, Time to progression (TTP), Progression-free survival (PFS), and overall survival (OS).

4.9.2. Response will not be considered evaluable in the following categories:

Patients have to receive at least 2 cycles of the combination of eribulin and grapiprant to be evaluated the response. The patients in the following categories are considered to be unevaluable for the response. Those patients who are not evaluable will be excluded from the response's statistical analysis and not be replaced.

Early Deaths:

Patients who die within the first 2 weeks of the initiation of proposed treatment. These cases will be considered treatment failures.

Lost to Follow-up:

Patients for whom there is inadequate information to judge tumor response because of loss of contact with our institution (> 2 months after a missed appointment) and referring physician despite repeated attempts to locate them. These cases will be considered treatment failures in the intent-to-treat analysis.

Major Protocol Violation:

Patients who significantly deviate from the treatment program by either adding or deleting another agent or another therapeutic maneuver or modifying the schedule substantially (delay treatment ≥ 7 days without administration reason) of the drug under evaluation. Patients who do not fulfill the requirements outlined under patient eligibility are also included in this category.

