Phase II adopts the Bayesian optimal phase II (BOP2) design with the null hypothesis H0: CBR = 10% versus the alternative hypothesis H1: CBR = 30%. If the phase II part starts with 300 mg dosing, we will enroll 6 patients and evaluate the clinical benefit in 12 patients (including 6 patients from the phase Ib cohort). For the purpose of futility monitoring, the assessment window for CBR is 24 weeks. If we observed 2 or more clinical benefits in 12 patients, we will proceed to enroll 13 patients and claim the study promising if we observed 5 or more clinical benefits in 25 patients. This design yields the power of 86% with the type I error of 10%.

If the phase II part starts with 200 mg dosing, we will enroll 5 patients and evaluate the clinical benefit in 11 patients (including 6 patients from the phase Ib cohort). If we observed 2 or more clinical benefits in 11 patients, we will proceed to stage 2. For stage 2, (a) if 3 patients treated at 300mg, we will enroll additional 11 patients, and we claim the study promising if we observed 4 or more clinical benefit in 22 (or 19) patients; and (b) if 6 patients treated at 300mg, we will enroll additional 8 patients and we claim the study promising if we observed 4 or more clinical benefit in 19 patients. The power of the design is 86% and 82%, respectively in case (a) and (b), given the type I error of 10%. The operating characteristics for the phase II portion of the trial are summarized in the **Table 7** below:

Table 7: The Operating Characteristics for Phase II

Scenario	Clinical Benefit Rate	Early Stopping (%)	Claim Promising (%)	Average Number of Patients (%)
1	0.1	65.9	8.3	16.4
2	0.2	27.5	52.0	21.4
3	0.3	8.5	86.4	23.9

Co-PI: [name] Date: 11/22/2022

[figure not shown]
Scenario	Clinical Benefit Rate	Early Stopping (%)	Claim Promising (%)	Average Number of Patients (%)
4	0.4	2.0	97.5	24.7
5	0.5	0.3	99.7	25.0

Product: Grapiprant Protocol 2021-0077 Proprietary Information of MD Anderson PI: [name]

Co-PI: [name]

Date: 11/22/2022

Figure 2. Trial design for phase Ib/II of grapiprant and eribulin treatment

Co-PI: [name] Date: 11/22/2022

The CBR and ORR will be summarized by frequency and percentage with 95% exact confidence intervals for all patients and by doses. Time to progression (TTP), progression-free survival (PFS), and overall survival (OS) will be summarized using the Kaplan-Meier method, including median with 95% confidence intervals.

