For each exploratory outcome measure (see 6.2, Biomarker Assessments), samples will be acquired pre- and post-treatment. Change associated with treatment will be assessed by t-test and regression models with relation to treatment time, with adjustment for relevant demographic and baseline covariates. A logistic regression model will be used to assess the association between objective response status and change in exploratory outcomes. A proportional hazard model will be used to assess the association between TTP, PFS, and OS with the change in urine prostaglandin E2 metabolite. Additional statistical methods may be used.

The Investigator is responsible for completing an efficacy/safety summary report and submitting it to the IND Office Medical Affairs and Safety Group, for review and approval.

Phase1b:

After the first 3 evaluable patients complete 1 cycle of study treatment, and every 3 patients thereafter. IND Office approval must be obtained, prior to expanding/changing dose levels.

Phase II:

Toxicity summary will be submitted after the first 9 evaluable patients (including the 6 patients treated at MTD), then every 6 evaluable patients complete 1 cycle of treatment.

Efficacy summary:

If the MTD is 300mg, summary will be submitted after 12 evaluable patients (including the 6 patients treated at MTD), complete 24 weeks of treatment and after the 25 evaluable patients complete 24 weeks cycles of treatment.

If the MTD is 200 mg, Summary will be submitted after 11 evaluable patients (including the 6 patients treated at MTD), complete 24 weeks of treatment, and after 25 evaluable patients complete 24 cycles of treatment.

A copy of the safety summary report should be placed in the Investigator's Regulatory Binder under "sponsor correspondence".

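### The 24-week boundary and clock for stable disease in the primary endpoint do not fit the futility window, the interim trigger or the scan schedule

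*Combined protocol and SAP*

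**What the plan says.** Section 4.1 defines the primary efficacy endpoint as "Clinical benefit rate (CBR): CR + PR + SD (>24weeks"). It dates time to progression, PFS and OS from first grapiprant, but gives clinical benefit no start date.

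Section 7.0 states: "For the purpose of futility monitoring, the assessment window for CBR is 24 weeks". For the 300 mg path, the efficacy "summary will be submitted after 12 evaluable patients (including the 6 patients treated at MTD), complete 24 weeks of treatment"; the 200 mg path uses 11 patients. The final 300 mg summary also refers to 24 weeks, in garbled wording, but the final 200 mg summary comes "after 25 evaluable patients complete 24 cycles of treatment".

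Section 4.3 says that phase II "adds 14 ± 2 days window period of grapiprant treatment alone before the main study". Scans are done at baseline, "after the 2 cycles of proposed treatment (does not includes window period), then at the end of every 3 cycles". Section 4.9.1 agrees: "after 2 cycles of proposed treatment (does not include window period) 3) every 3 cycles of proposed treatment". Footnote c of both study calendars (section 4.13) labels the scans C3, C6, C9 and C12, and describes the later ones as falling at the end of every three cycles.

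The look at 12 pools 6 phase Ib patients, who have no lead-in, with 6 phase II patients, who have one. The trial goes on with 2 or more benefits in 12 and is called promising with 5 or more in 25.

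**The concern.** Three items must agree before a patient with stable disease can be counted: the boundary (beyond 24 weeks, or at 24 weeks), the day the clock starts, and the scan that shows the status. Here they do not agree. Taken literally, stable disease of more than 24 weeks cannot be shown inside a 24-week window when the deciding scan falls on day 168. If the 24 weeks run from first grapiprant, a phase II patient reaches the trigger before that scan.

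The threshold at the look is 2, so one or two uncounted benefits can decide whether the trial stops. The trial is single-arm and open-label. A definition chosen once the count is known would also be hard to defend.

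**Working it through.** **1. Table 7 reproduced (300 mg path).** Inputs from section 7.0: go on if at least 2 of 12; promising if at least 5 of 25; rates 10% and 30%.

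- Stop at 30%: 0.7^12 + 12 × 0.3 × 0.7^11 = 0.0138 + 0.0712 = 0.0850. Table 7: 8.5%.
- Promising at 30%: sum over x = 2 to 12 of P(X12 = x) × P(X13 ≥ 5 − x) = 0.8635. Table 7: 86.4%, equal within rounding or simulation error.
- At 10%: stop 65.9%, promising 8.3%. Both match.

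**2. Calendar.** A cycle is 21 days and the lead-in is 14 ± 2 days (section 4.3).

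- Scans after cycles 2, 5, 8 and 11 fall on days 42, 105, 168 and 231 from C1D1, that is weeks 6, 15, 24.0 and 33.
- In phase II the cycle-8 scan is 168 + 12 to 168 + 16 = 180 to 184 days from first grapiprant, that is weeks 25.7 to 26.3.
- Day 168 from first grapiprant is day 152 to 156 from C1D1. The last scan by then is the one on day 105, week 15 from C1D1.
- Cycle delay: section 4.4.2 allows the day 8 eribulin dose to move to day 15, and then to "initiate the next cycle no sooner than 2 weeks later". The next cycle starts on day 29 instead of day 22. One such delay puts the cycle-8 scan on day 175. If stable disease is dated to the scan that shows it, day 168 fails the strict boundary and day 175 passes.
- Other reading: the literal end of cycle 9 is 9 × 21 = day 189 (week 27). The footnotes tie the first scan, after 2 cycles, to the label C3. C9 therefore more likely means after cycle 8.
- 24 cycles × 21 = 504 days = 72 weeks.

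**3. How many of the 12 could be affected.** The documents give no accrual rate. If 25 patients accrue evenly over 24 to 36 months (an assumption; section 1.0 gives only the trial duration), the number still waiting is about 1 + gap × rate.

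- Gap of 2 weeks (0.46 months; trigger dated from first grapiprant): 1 + 0.46 × 25/36 = 1.3 to 1.5 with 25/24.
- Gap of 9 weeks (2.07 months; stable disease at day 168 refused, next scan at week 33): 2.4 to 3.2. With accrual over 18 to 30 months it is 2.7 to 3.9.

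**4. Effect at the look, true CBR 30%.** Let h of the 12 have stable-disease benefit that cannot be counted at the look but counts at the end. These h patients show benefit only through CR or PR, at rate r (assumed; the documents give none). With m = 12 − h:

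stop = (1 − r)^h × [0.7^m + m × 0.3 × 0.7^(m−1)] + h × r × (1 − r)^(h−1) × 0.7^m

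Example, h = 3 and r = 0.10: 0.729 × 0.1960 + 3 × 0.10 × 0.81 × 0.0404 = 0.1429 + 0.0098 = 0.153. Power comes from the same enumeration, with the look passed on visible benefits and the final count on all benefits.

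| h | r = 25%: stop / power | r = 10%: stop / power | r = 0: stop / power |
|---|---|---|---|
| 0 | 8.5% / 86.4% | 8.5% / 86.4% | 8.5% / 86.4% |
| 1 | 9.0% / 86.0% | 10.4% / 84.9% | 11.3% / 84.1% |
| 2 | 9.5% / 85.6% | 12.6% / 83.0% | 14.9% / 81.1% |
| 3 | 10.0% / 85.2% | 15.3% / 80.7% | 19.6% / 77.0% |

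At a true CBR of 10% with h = 3 and r = 5%, the chance of a promising claim is 7.5% against 8.3%, so type I error goes down. On the 200 mg path (at least 2 of 11), the false stop is 11.3% with nothing hidden. It is 11.9%-13.7% for h = 1 and 13.2%-20.0% for h = 3, with r from 25% down to 10%.

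**The case against.** The best defence is that the futility window already shows the intent: stable disease at the 24-week scan counts. The trigger is also a not-before condition for a report to the IND Office, so the team may wait for the scan. Both points are fair, but waiting is permitted and not required. The window statement covers futility monitoring only and does not change the strict sign in section 4.1.

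The boundary problem also depends on how stable disease is ended. If it runs to progression, as time to progression does, a patient stable on day 168 progresses only later and passes. Section 4.1 does not say which convention applies. On the day-189 reading the boundary problem disappears, but the scan then falls still later than the 24-week trigger. The calendars carry a ±3-day scheduling window for treatment weeks; whether it covers imaging is not stated.

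A reader might infer more than the documents support:

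- **Inflated type I error.** On a first-grapiprant clock, a phase II patient who progresses at the cycle-8 scan (about week 26) might be called stable for more than 24 weeks. That needs a clock that section 4.1 does not give to this endpoint, progression counted as benefit, and a frequency that appears nowhere. Responses follow RECIST with an independent imaging read (section 4.3). It also requires stable disease to run up to the progression scan, the convention under which the boundary problem vanishes.
- **No phase II stable disease can count at the look.** With all six hidden and no responders, the false stop would be 0.7^6 + 6 × 0.3 × 0.7^5 = 42%. Nothing says that later scans are disregarded, and phase II patients enrolled earlier may already have had theirs.
- **The final analysis has only the section 4.1 definition.** The garbled 300 mg final trigger in section 7.0 is also a 24-week criterion.

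**Conclusion.** The point holds as a conflict between stated rules for the primary endpoint, and it should be settled before the look at 12 patients. Table 7 is not wrong; it rests on every benefit being countable when the look is taken.

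For 1 to 3 affected patients the effect is modest for response rates of 25% to 10%: at most 6.8 points more false stopping (15.3 − 8.5) and 5.7 points less power (86.4 − 80.7). With no responders at all it reaches 11.1 and 9.4 points. These sizes depend on the assumed number of affected patients, the response rate and the accrual. They are not upper bounds: slower responses or faster accrual would give more. The error runs toward stopping an active treatment, not toward a false claim.

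The 24-cycle trigger for the final 200 mg summary is a separate conflict: 72 weeks against the 24 weeks used elsewhere.

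**What to change.** - Define clinical benefit as a best response of CR or PR, or stable disease without progression through the scan after cycle 8 (nominally at least 24 weeks from C1D1).
- Use this clock and definition for phase Ib and phase II patients alike, at the look and in the final analysis.
- State that the calendar's ±3-day window applies to this scan, or give another tolerance.
- Hold the look until each of the 12 (or 11) patients has had that scan, has already responded or has already failed.
- Align the futility window and the summary triggers in section 7.0 with this, and reconcile 24 cycles with 24 weeks.
- Make the scan labels in both calendar footnotes agree with sections 4.3 and 4.9.1.

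The cost is protocol and SAP wording, with no added scans if the cycle-8 reading is the intended one. The amendment must declare the change from more than 24 weeks to at least 24 weeks. Clinical benefit will run on a different clock from time to progression, PFS and OS. The interim may move by about 2 weeks, or longer where cycles were delayed.

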4.2 Entry Criteria

To be eligible for participation in this trial, the subject must meet the following criteria.

4.2.1 Inclusion Criteria

- 1. Male or female \geq 18 years of age.
- 2. Is willing and able to provide written informed consent for the trial.

Co-PI: [name] Date: 11/22/2022

3. Has histological confirmation of breast carcinoma with a clinical diagnosis of IBC based on the presence of inflammatory changes in the involved breast, including diffuse erythema and edema (peau d'orange), with or without an underlying palpable mass involving the majority of the skin of the breast. Or the diagnosis confirmed by the MD Anderson IBC specialists. Pathological evidence of dermal lymphatic invasion should be noted but is not required for the diagnosis of IBC.

- 4. Any prior treatments will be allowed except eribulin and/or any EP2/4 inhibitor.
- 5. Has at least 2 weeks of untreated period from the previous treatment.
- 6. Any receptor status for ER/PR and HER2. But for HER2+ type, must has failed trastuzumab, pertuzumab, and T-DM1 treatment.

NOTE:

HER2 positive status is defined as strongly positive (3+) staining score by IHC, or gene amplification using FISH, if performed. If IHC is equivocal (2+), please refer to Appendix H for current ASCO guidelines algorithm for evaluation of HER2.

HER2 negative status, which is determined by assays using IHC require negative (0 or 1+) staining score. If IHC is equivocal (2+) staining score, please refer to Appendix H for current ASCO guidelines algorithm for evaluation of HER2.

7. Has a measurable disease per RECIST v1.1 (only applies to phase II part).

NOTE:

Measurable disease: Measurable lesions are defined as those that can be accurately measured in at least one-dimension (longest diameter to be recorded) as ≥ 20 mm by chest X-ray, ≥ 10 mm by computed tomography (CT) scan, ≥ 10 mm with calipers by clinical exam.

Measurable malignant lymph nodes: To be considered pathologically enlarged and measurable, a lymph node must be ≥ 15 mm in short axis when assessed by CT scan.

Non-measurable disease: All other lesions (or sites of disease), including small lesions, are considered non-measurable. Bone lesions, leptomeningeal disease, ascites, pleural/pericardial effusions, lymphangitis, cutis/pulmonitis, inflammatory breast disease, and abdominal masses [not followed by CT or magnetic resonance imaging (MRI)] are considered non-measurable.

- 8. Has a distant metastasis site or locoregional recurrence.
- 9. Is willing to provide fresh tumor tissue via tumor biopsy before the first dose of the study drug only if participant has a disease can be be safely accessed through a CT-guided/US-guided or percutaneous biopsy for multiple core biopsies judged by the investigator. If participant doesn't have a disease that can be safely accessed, they are still eligible.

Co-PI: [name] Date: 11/22/2022

- 10. Performance status (PS) of 0 to 2 on the Eastern Cooperative Oncology Group (ECOG) performance scale
- 11. Has adequate organ function as determined by the following laboratory values:
 - Absolute neutrophil count (ANC) $\geq 1,200 \text{ /mcL}$
 - Platelets $\geq 100,000 / \text{mcL}$
 - $Hgb \ge 9 g/dL$
 - Total bilirubin ≤ 1.5 x upper limit of normal (ULN) (up to ≤ 3 x ULN for patients with liver metastasis)
 - ALT and AST ≤ 2.5 x ULN (up to ≤ 5 x ULN for patients with liver metastasis)
 - Cockcroft-Gault GFR (mL/min/1.73 m²) \geq 50. Cockcroft-Gault GFR Creatinine Clearance Value = $[(140\text{-age}) \times \text{weight (kg)}]/(\text{Scr} \times 72) \times (0.85 \text{ for females})$.
- 12. Left ventricular ejection fraction (LVEF) \geq 50% by ECHO or MUGA scan.
- 13. Female patients must not be pregnant or breastfeeding and must be practicing a medically acceptable form of locally approved birth control, be sterile or post-menopausal. Male patients should be using a medically acceptable form of birth control during the trial or be sterile.
 - o Female patient: A female patient is eligible to participate if she is not pregnant, not breastfeeding, and at least one of the following conditions applies:
 - Not a woman of childbearing potential (WOCBP)

OR

- A WOCBP agrees to follow the contraceptive guidance during the treatment period and at least 6 months after the last dose of trial intervention and must refrain from breastfeeding for at least 2 months after the last grapiprant treatment.
- Additionally, WOCPB must have a negative urine pregnancy test no more than 7 days prior to starting treatment on-study.
- Male patients: A male patient must agree to use contraception during the treatment period and for at least 6 months after the last grapiprant treatment and refrain from donating sperm during this period.
- 14. Patient with known HIV including current or prior infection would be included if:
 - with CD4+ T-cell (CD4+) counts \geq 350 cells/uL
 - without a history of AIDS-defining opportunistic infections

